25 REMUNERATION PLAN

Subjects will not be compensated for the time and inconvenience of study participation, including for any outpatient assessments that may occur following hospital discharge.

26 ASSESSMENT OF SAFETY

Regulatory requirements, including FDA regulations and ICH Guideline for Good Clinical Practice, set forth safety monitoring and reporting responsibilities of Sponsors and Investigators to ensure the safety and protection of human subjects participating in clinical trials.

Documenting, Recording, and Reporting Adverse Events

At each contact with the subject, information regarding serious adverse events will be elicited by appropriate questioning and will be:

- documented in the subject's medical record/source document,
- recorded on the Serious Adverse Event Case Report Form (SAE CRF), and
- reported to relevant regulatory authorities by the principal investigator or designee as outlined below

Definitions

Adverse Event (AE)

An adverse event is any untoward or unfavorable medical occurrence in a human subject, including any abnormal sign (e.g., abnormal physical exam or laboratory finding), symptom, or disease, temporally associated with the subject's participation in the research, whether or not considered related to the research.

Serious Adverse Event (SAE)

A Serious Adverse Event is an AE that results in one or more of the following outcomes:

- death
- a life threatening (i.e., an immediate threat to life) event

- prolongation of the existing hospitalization (or re-hospitalization)
- a persistent or significant incapacity or substantial disruption of the ability to conduct normal life functions
- a congenital anomaly/birth defect
- a medically important event*

* Medical and scientific judgment should be exercised in deciding whether expedited reporting is appropriate in other situations, such as important medical events that may not be immediately life threatening or result in death or hospitalization but they may jeopardize the subject or may require intervention to prevent one of the other outcomes listed above.

Protocol Deviation: Any change, divergence, or departure from the IRB approved study procedures in a research protocol. Protocol deviations are designated as serious or non-serious and further characterized as

- 4. Those that occur because a member of the research team deviates from the protocol.
- 5. Those that are identified before they occur, but cannot be prevented.
- 6. Those that are discovered after they occur

Serious Protocol Deviation: A deviation that meets the definition of a Serious Adverse Event or compromises the safety, welfare or rights of subjects or others.

Non-compliance: The failure to comply with applicable NIH HRPP policies, IRB requirements, or regulatory requirements for the protection of human subjects. Non-compliance is further characterized as

- 4. Serious: Non-compliance that
 - a. Increases risks, or causes harm, to participants
 - b. Decreases potential benefits to participants
 - c. Compromises the integrity of the NIH-HRPP
 - d. Invalidates the study data
- 5. Continuing: Non-compliance that is recurring
- 6. Minor: Non-compliance that, is neither serious nor continuing.

Assessment of Safety

Safety data in this study will be limited to the collection of targeted symptoms (daily, while hospitalized or in an ETU) and SAEs. Until participants are discharged from the hospital or ETU, items on the targeted list do not additionally need to be reported as SAEs.

The Data Coordinating Center will grade the severity of laboratory values according to the Division of AIDS Table for Grading the Severity of Adult and Pediatric Adverse Events Version 2.0, 2014.

Investigator Assessment of Serious Adverse Events

Due to severity of critical illness in Ebola disease and expected clinical progression, for clinical events, investigators will capture only SAEs and a targeted list of current symptoms and conditions. The Investigator will evaluate all SAEs with respect to **Seriousness** and **Causality** (relationship to study agent and relationship to research) as defined below.

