21.4.1 Baseline Evaluation

Within 24 hours prior to randomization, a baseline clinical evaluation will be performed with documentation of current symptoms and clinical conditions including vital signs.

The list of symptoms and signs to assess includes: fever, sore throat, cough, fatigue, weakness, dizziness, confusion, hearing loss, headache, myalgia, arthralgia, loss of appetite, vomiting, diarrhea, symptoms, abdominal pain, trouble urinating, chest pain, breathing difficulties, shortness of breath, hiccups, rash, edema, conjunctivitis, oral ulcers/thrush, hemorrhage, multi-organ failure, convulsions.

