21.4.4 Study Drug Administration Timing

It is possible that Study Day 0 may be consumed by longitudinal determination of a patient's overall clinical status, implementation of oSOC provisions, assessment for study eligibility, and study randomization. Therefore, it is possible that actual administration of an investigational study intervention (if part of the assigned treatment arm) may be deferred until Study Day 1. Refer to the Pharmacy SOP for specific administration details.

Follow Up Study Days

The plan for study drug administration, clinical assessments, and lab monitoring are outlined in the Schedule of Evaluations. Details are below on assessments are as follows:

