26.4.1 Causality

The likelihood that the SAE is related to the study agent will be assessed by the investigator considering by the following simplified categorization. Due to the severity of Ebola illness and limitations of an ETU, further detailed breakdown will not occur:

Reasonable Possibility

- reasonable temporal relationship
- little evidence for a more likely alternative etiology

No Reasonable Possibility

• does not have a reasonable temporal relationship

OR

• reasonable evidence for a more likely alternative etiology

Investigator Reporting Responsibilities to the Sponsor

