26.9.1 Investigator Safety Monitoring

The Investigator or designee may interrupt the administration of study drug to an individual subject if indicated for unanticipated problems or SAEs. In addition, the Investigators are responsible for:

- Protecting the safety and welfare of subjects
- Evaluating subject safety
- Notifying the sponsor of SAEs and immediately-reportable events
- Informing the IRB/IEC of SAEs, as per institutional requirements

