26.9.3 Data and Safety Monitoring Board (DSMB)

An independent DSMB will review the study no less frequently than twice a year. The DSMB may convene additional reviews as necessary, dependent on the rate of subject accrual. The DSMB will review the study data to evaluate the safety, efficacy, study progress, and conduct of the study. All SAEs, all unanticipated problems, and all IND Safety Reports will be reported by the Data Coordinating Center to the DSMB at the same time they are submitted to the IRB or IND Sponsor. The PI will submit the written DSMB summary open reports with the DSMB recommendations to the IRB.

- The DSMB will monitor safety closely throughout the trial and may pause enrollment in the event of study-related deaths or SAEs that are considered study-related.
- The DSMB will also review the completeness of follow-up and other aspects of study conduct.
- After each meeting they will recommend continuing the study as planned, modifying the study, or terminating the study.

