3.7 ZMapp Infusion Summaries

Note: for patients assigned to the ZMapp group, ZMapp was to be started immediately following randomization. The 2nd dose was to be given 3 days after the 1st dose; the 3rd dose was to be given 3 days after the 2nd dose.

- The distribution of the number of infusions per patient (0, 1, 2, 3)
- Time elapsed between randomization and first dose
- Study day of infusion of each dose will be summarized
- Duration (minutes and mean) by study day
 - additional separate tables for adults and children
- Volume received (mean and ml/kg) by study day.
- Percent receiving prepared volumes of 95% or greater.
- Calculated dose (mg/kg) of ZMapp Dose actually administered
- Number and percent of patients experiencing infusion reactions
 - o Total N (%)
 - \circ N (%) categorized by the specific infusion reactions reported
 - N (%) which required intervention
 - N% by intervention taken
- Number and percent of patients experiencing infusion interruptions

- Total N (%)
- Pre-treatments administered before infusions to ameliorate reactions
- Other problems with the infusion noted on the case report form.
- Listing of other problems related to infusion
- Listing of subjects assigned to ZMapp who did not receive all doses before death: subject ID, site, days from randomization to first dose, days from first ZMapp to death, total doses given

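### Section 26 lets a serious targeted-list event suspected to be drug-related go unfiled as an SAE until discharge, a period that normally spans all three ZMapp doses

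*Combined protocol and SAP*

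**What the plan says.** The combined file holds two protocol texts. This point concerns the amended one (sections 16 to 29) and the two data analysis plans.

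- **Exemption.** Section 26 restricts clinical safety data to a daily targeted symptom record plus SAEs, citing the severity and expected course of the disease. It adds: "Until participants are discharged from the hospital or ETU, items on the targeted list do not additionally need to be reported as SAEs".
- **List.** The only symptom list in the documents is in section 21.4.1. It opens with fever and ends with "breathing difficulties, shortness of breath, hiccups, rash, edema, conjunctivitis, oral ulcers/thrush, hemorrhage, multi-organ failure, convulsions". That section does not call it the targeted list.
- **Causality.** Section 26.4.1: "The likelihood that the SAE is related to the study agent will be assessed by the investigator".
- **Reporting.** Section 26.5.1 requires every SAE to be reported: deaths and immediately life-threatening events within 1 business day, others within 3. It has the medical monitor judge expectedness and makes every death an SAE. Section 21.5.1 lists current symptoms and any SAE as separate daily entries.
- **Oversight.** Under section 26.9.3 the DSMB "may pause enrollment in the event of study-related deaths or SAEs that are considered study-related". Under section 26.9.1 the investigator "may interrupt the administration of study drug to an individual subject if indicated for unanticipated problems or SAEs".
- **Dosing.** Final plan, section 3.7: "ZMapp was to be started immediately following randomization", and "The 2nd dose was to be given 3 days after the 1st dose; the 3rd dose was to be given 3 days after" the second. Protocol section 21.4.4 says administration "may be deferred until Study Day 1".
- **Reports.** Table A3.1 of the first data analysis plan has two event-driven safety rows going to the DSMB and LeafBio: treatment-related SAEs, and Safety Reports. The content of the second is not defined.

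**The concern.** Not filing every expected Ebola symptom as an SAE is sensible in an Ebola treatment unit. The difficulty is the criterion. The waiver depends on where the patient is, not on whether the event is serious or thought to be caused by the drug. The time in the unit is also the time of dosing, and the protocol itself says human safety data on these agents are scarce. Establishing safety is part of the primary objective, and infusion reactions are secondary endpoints (section 18.2.2).

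Two things are at stake. One is speed: a drug-suspected serious event may be seen at the next DSMB meeting and not within days. The other is interpretation: a low count of related SAEs would partly reflect the reporting rule.

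**Working it through.** The plan gives no figure to reproduce. The check is a dosing-day count, then a trace of one event through the reporting rules.

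**1. Which doses fall under the waiver.** With the first dose on Day d, doses fall on d, d+3 and d+6.

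- d = 0 gives Days 0, 3, 6.
- d = 1 gives Days 1, 4, 7.

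Table 9 places all ZMapp doses in the Day 0 to 7 columns, ahead of the column for Day 8 onward while hospitalized. Section 3.9.1 of the final plan says the first 3 days were free of discharges. Section 3.9 gives 13/49 = 26.5% of discharges after more than 16 days. The earliest discharge day is not stated. So dose 1 is covered for certain, and doses 2 and 3 are covered for any patient still in the unit, which is the normal case.

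**2. Trace of one event.** Take a non-fatal, life-threatening convulsion in the unit that the investigator suspects is due to the drug, recorded only as a targeted symptom.

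| Safeguard | Triggered by | Reached if no SAE is filed? |
|---|---|---|
| Causality (26.4.1) | SAE | No |
| Expectedness (26.5.1) | SAE | No |
| 1- or 3-business-day clock (26.5.1) | SAE | No |
| Event-driven related-SAE report (Table A3.1) | Related SAE | No |
| DSMB pause ground (26.9.3) | Study-related death or SAE | No |
| Unanticipated-problem report, 7 calendar days (26.5.2) | Unexpected, related and of greater risk | Only if all three hold |
| Symptoms by arm (first plan, 4.5.4) | Symptom record | Yes, by meeting |
| Infusion reactions by type (first plan, 4.6.4) | ZMapp infusion form | Yes if entered there, by meeting |

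Unexpectedness in section 26.5.2 is judged against people with life-threatening Ebola, a test that a listed Ebola symptom may well fail.

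**3. What the remaining records carry.** Section 26 provides severity grading for laboratory values only, and the final plan compares symptoms by number and by days (3.9.1). A mild and a life-threatening convulsion therefore count alike in that comparison. The patient profiles (first plan, 4.3) show infusion days and SAEs but do not list infusion reactions. The final plan (3.7) does tabulate reactions that needed intervention, but without relatedness.

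**4. Size of the delay.** Section 26.9.3 sets a floor of two DSMB reviews a year. Seven took place after the first randomization on March 13, 2015. Their dates are not given. Up to the planned closure on January 14, 2016 there are 307 days, and 307/7 = 44 days, so roughly one review every six weeks. The comparison is weeks against 1 or 3 business days.

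**5. Conflict in the text.** Section 26.5.1 requires all SAEs to be reported and section 21.5.1 requires any SAE to be recorded daily. Nothing says which rule governs when a listed item meets a seriousness criterion.

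**The case against.** The strongest defence is that the exemption is deliberate and reasoned, and that its wording waives only duplicate reporting. On that reading a life-threatening event is still an SAE under section 26.5.1, and an investigator remains free to file it. The case report forms, Pharmacy SOP and Reporting SOP are not in the documents and may settle the matter. The wording does allow this reading. It does not compel it, and a site that filed nothing could point to section 26 as its authority.

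Several stronger readings are tempting and do not stand:

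- A reader might infer that prompt safety reporting is switched off during dosing. It is not. Deaths and serious events outside the list remain SAEs (anaphylaxis and hypotension are not on the list), unanticipated problems go to the DSMB, and Table A3.1 has a separate event-driven Safety Reports row.
- A reader might infer that the DSMB never learns of these events. It sees symptoms by arm and infusion reactions by type at its meetings.
- A reader might infer that no ground for interrupting a dose is left. Section 26.9.1 also names unanticipated problems, and its wording is permissive.
- A reader might take twice-yearly review as the actual delay. It is a minimum, and reviews were far more frequent.

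One further objection stands in full. The trial is open-label and only one arm is infused. A rule making every serious listed event within a fixed time of an infusion an SAE would also catch Ebola itself, in the ZMapp arm only, and would bias the between-arm SAE tests. That rules out an automatic window.

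**Conclusion.** The concern holds in limited form. A non-fatal, serious, listed event that the investigator suspects is due to study drug can stay outside the SAE route while the patient is in the unit. It then misses five safeguards keyed to SAEs: causality, expectedness, the 1- or 3-business-day clock, the event-driven related-SAE report and the DSMB's stated pause ground. On the nominal schedule this normally covers all three ZMapp doses. Such events are delayed and lack a recorded causality assessment, but they are not lost. They would be missing from the SAE comparison and the related-SAE count (first plan, 4.6.1; final plan, 3.9.2).

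This rests on two assumptions: that the section 21.4.1 list is the targeted list, and that no unseen form or SOP already makes the exception. The documents do not show how many events were affected.

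**What to change.** Reconcile section 26 with sections 21.5.1 and 26.5.1 by one added sentence. It should say that a targeted-list item which meets a seriousness criterion, and which the investigator judges to have a reasonable possibility of relation to study agent under section 26.4.1, is still reported as an SAE before discharge. It should cover serious reactions recorded on the study-agent infusion form. Name the targeted list explicitly. Do not use an automatic time window.

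In the final analysis plan, flag these reports and present the between-arm SAE comparison with and without them. State the exemption beside any related-SAE count. For patients treated before the change, that note is the minimum needed.

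The cost is the sentence, a memo to sites and a few extra SAE forms. These would fall mostly in the ZMapp arm, which is why the paired presentation is needed.

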26.4.1 Causality

The likelihood that the SAE is related to the study agent will be assessed by the investigator considering by the following simplified categorization. Due to the severity of Ebola illness and limitations of an ETU, further detailed breakdown will not occur:

Reasonable Possibility

- reasonable temporal relationship
- little evidence for a more likely alternative etiology

No Reasonable Possibility

• does not have a reasonable temporal relationship

OR

• reasonable evidence for a more likely alternative etiology

Investigator Reporting Responsibilities to the Sponsor

26.5.1 Serious Adverse Events

All SAEs must be reported on the Serious Adverse Event case report form (SAE CRF). Deaths and immediately life threatening SAEs must be reported within 1 business day after the site becomes aware of the event to the Data Coordinating Center. All other SAEs must be reported within 3 business days of site awareness. All deaths must be reported as SAEs.

The medical monitor, in consultation with the site investigator, will determine the expectedness of all SAEs.

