3.8 Primary Outcome

The primary outcome is death within 28 days from randomization, and the primary population includes all randomized patients, with the exception of one individual who fled from the ETU on the first day and for whom no other primary data were subsequently captured.

Note: as a sensitivity analysis to assess the impact of the single subject with unknown vital status following randomization, the primary analysis described below will be performed assuming the subject was alive at 28 days and repeated assuming the subject was dead at 28 days.

Primary analysis

Inference relating to the primary endpoint will quantify the probability that the 28-day mortality rate is lower (or higher) under ZMapp relative to oSOC using the Bayesian paradigm as follows:

- A. The prior distribution of 28-day mortality probabilities, p₀ and p₁, in the oSOC and ZMapp arms is that of independent uniforms on [0,1].
- B. The posterior distributions of p₀ and p₁ after observing x₀ and x₁ deaths among n₀ and n₁ people in the two arms is that of independent betas with respective parameters (x₀+1, n₀-x₀+1) and (x₁+1, n₁-x₁+1).
- C. The posterior probability that p₁<p₀ will be computed: if this probability is 0.975 or greater, ZMapp will be declared superior to oSOC, whereas if the probability is 0.025 or less, ZMapp will be declared inferior to oSOC.
- D. Treatment effect estimates and 95% credible intervals will be computed for both the relative risk p_1/p_0 and absolute risk difference p_1-p_0 . The medians of the posterior distributions of p_1/p_0 and p_1-p_0 are used to estimate these quantities. 95% credible intervals are computed as follows.
 - a. For p_1/p_0 , compute lower and upper limits (L and U, respectively) satisfying $P(p_1/p_0 \le L \text{ given } x_0, x_1) = 0.025$ and $P(p_1/p_0 \ge U \text{ given } x_0, x_1) = 0.025$.
 - b. For p₁-p₀, compute lower and upper limits (L and U, respectively) satisfying P(p₁-p₀<L given x₀,x₁)=0.025 and P(p₁-p₀>U given x₀,x₁)=0.025.

Additional Supportive Analyses Using Primary Outcome:

Alternative test statistics:

The following alternative test statistics will be performed on the primary outcome as secondary analyses.

- Barnard's unconditional test will be performed using a one-tailed test of p₁=p₀ versus p₁<p₀.
 - A. The first alpha level used is 0.025 (one-sided). As with the Bayesian analysis, the overall type 1 error rate including monitoring may exceed 0.025.

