3.9.2 Safety-Related Outcomes

- SAEs will be summarized and compared between treatment groups as follows:
 - Number and percent of patients experiencing SAEs by treatment group. Test of statistical significance will use Fisher's exact test.
 - For SAEs that are assessed as related to study drug, counts by treatment groups and p-value from zero-inflated negative binomial model.
- Safety line listings by treatment group will be provided for SAEs and "unanticipated problems". Listings will include treatment group label, diagnosis, relatedness to treatment, date of onset, time from treatment to onset, event status (recovered/resolved, recovering/resolving, not recovered/not resolved, recovered/resolved with sequelae, death), date of resolution or death, and EVD status.
- Unanticipated problems

Incidence of "unanticipated problems" will be tabulated for each of the treatment groups. Reports will have similar format as the summary reports for SAEs.

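### The any-SAE comparison is likely to be dominated by deaths and could mask an excess of non-fatal SAEs on ZMapp if ZMapp lowers mortality

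*Combined protocol and SAP*

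**What the plan says.** **Definition and reporting (amended protocol).** Section 26 defines the term: "A Serious Adverse Event is an AE that results in one or more of the following outcomes", and death is the first outcome listed. Section 26.5.1 adds: "All deaths must be reported as SAEs". Deaths from Ebola itself are not excepted.

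**What need not be reported as an SAE.** Section 26, Assessment of Safety, limits clinical safety data to SAEs and a daily list of targeted symptoms. Until discharge from the hospital or treatment unit, "items on the targeted list do not additionally need to be reported as SAEs". That section does not enumerate the targeted list. The symptoms and conditions to be assessed under Section 21.4.1 end with "hemorrhage, multi-organ failure, convulsions".

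**Analysis (Final Data Analysis Plan, 3.9.2).** There are two SAE tests. One covers all SAEs: "Number and percent of patients experiencing SAEs by treatment group. Test of statistical significance will use Fisher's exact test". The other is restricted to events judged drug-related, and compares their number between arms with a zero-inflated negative binomial model.

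Neither separates fatal from non-fatal events. Nor does Section 4.6.1 of the Data Analysis Plan for MCM RCT, which covers the DSMB reports; its SAE-rate model for all SAEs and its Kaplan-Meier SAE curves are not carried into the final plan.

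**Primary endpoint (Final Data Analysis Plan, 3.8).** "The primary outcome is death within 28 days from randomization". The same section notes, from pooled data, that every death fell within the first 8 days.

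**The concern.** Safety is half of the primary objective (protocol Section 17; Final Data Analysis Plan, Section 2). The any-SAE test is the plan's one randomised comparison of all serious events. Every primary-endpoint death enters it, while some serious in-hospital events that patients survive are recorded on the daily forms and need not enter it.

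The SAE percentage therefore moves largely with mortality. If ZMapp saves lives, its SAE percentage falls for that reason alone, and a real excess of non-fatal serious events can be offset. The any-SAE result then says little about toxicity, in either direction.

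**Working it through.** **Inputs from the documents**
- 72 patients randomised 1:1 (Final Data Analysis Plan, Section 2), so about 36 per arm.
- Planning mortality pairs 0.20 v 0.40 and 0.30 v 0.50 (protocol Section 22, Power and Sample Size).
- Pooled mortality of about 30%. This is inferred: the plan reports viral clearance in 49 or 50 patients, and one patient has no outcome. If every survivor cleared, 21 or 22 of the remaining 71 died (71 less 50, or 71 less 49), that is 30% or 31%.

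**Assumption.** The non-fatal SAE rate is not given. Let q be the probability that a survivor has a reported SAE. It was varied over 2%, 5% and 10% in both arms, and up to 40% on ZMapp against 5% on oSOC.

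**Step 1: the plan's own figures.** No power is stated for the SAE comparison, so the mortality power was checked. The Bayesian sequential rule, with looks from 6 to 20 per arm and then at every 20 up to 100, and thresholds 0.999 interim and 0.975 final, gives 0.879 for 0.20 v 0.40 and 0.834 for 0.30 v 0.50. The protocol states 88% and 83%, so these are reproduced.

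**Step 2: share of SAE patients who are deaths.** With mortality d, P(any SAE) = d + (1 − d)q. The share is the sum of d over both arms divided by the sum of P(any SAE).

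| Mortality, ZMapp v oSOC | q = 2% both | q = 5% both | q = 10% both | q = 40% v 5% |
|---|---|---|---|---|
| 0.30 v 0.30 | 96% | 90% | 81% | 66% |
| 0.20 v 0.40 | 96% | 90% | 81% | 63% |
| 0.30 v 0.50 | 97% | 93% | 87% | 72% |

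Lowest cell: mortality sums to 0.60 and P(any SAE) to 0.95 (0.52 plus 0.43), so the share is 63%. If 40% of survivors in both arms had an SAE, P(any SAE) in the 0.20 v 0.40 row would sum to 1.16 (0.52 plus 0.64) and the share would fall to 52%. At 30% mortality, deaths drop below half only when 0.70q exceeds 0.30, that is q above 43%.

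**Step 3: what each test would show.** Exact power of the two-sided 5% Fisher test at 36 per arm, with q = 5% on oSOC. The non-fatal event probability is (1 − d)q.

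| Mortality, ZMapp v oSOC | q on ZMapp | Any SAE, ZMapp v oSOC | P(any-SAE test shows harm) | P(non-fatal test shows harm) |
|---|---|---|---|---|
| 0.20 v 0.40 | 20% | 36% v 43% | 0.002 | 0.28 |
| 0.20 v 0.40 | 25% | 40% v 43% | 0.006 | 0.48 |
| 0.20 v 0.40 | 30% | 44% v 43% | 0.015 | 0.67 |
| 0.30 v 0.30 | 25% | 47.5% v 33.5% | 0.15 | 0.32 |
| 0.30 v 0.30 | 30% | 51% v 33.5% | 0.23 | 0.49 |

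If q applies to all patients, including those who later die, the non-fatal test has power 0.57 at 25% v 5% and 0.76 at 30% v 5%.

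With no excess non-fatal harm (q = 5% in both arms, mortality 0.20 v 0.40), the any-SAE test favours ZMapp with probability 0.31. That is the mortality effect alone.

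**Step 4: a worked case.** Take 36 per arm, deaths 7 on ZMapp and 14 on oSOC, and survivors with a non-fatal SAE 7 and 0. Any SAE is 7 plus 7, so 14 patients on ZMapp, against 14 plus 0, so 14 patients on oSOC; Fisher p = 1.00. Non-fatal SAEs are 7/36 against 0/36; p is 2 × C(36,7)/C(72,7), which is 0.011. Among survivors they are 7/29 against 0/22; p is [C(29,7) + C(22,7)]/C(51,7), which is 0.015.

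**The case against.** **Other outputs bear on non-fatal harm.** The final plan also has a test of drug-related SAE counts, SAE listings by arm with event status, Wilcoxon comparisons of symptom counts over 28 days and over 3 days, laboratory summaries, and infusion reactions. With 72 patients, a reader of the listings could separate fatal from non-fatal SAEs by hand. This stands: a reader might infer that the trial's safety assessment as a whole would miss non-fatal harm, and the documents do not support that. But none of these outputs is a randomised comparison of non-fatal SAEs. Relatedness is an investigator's judgement (protocol 26.4.1) in an open-label trial whose controls receive no study drug. Infusion reactions are summarised for ZMapp only. The symptom tests count symptoms without weighting severity.

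**Targeted conditions are recorded elsewhere.** They go on the daily forms and are not lost. Protocol 18.2.2 lists progression to severe disease (haemorrhage, multi-organ failure, seizures) as a secondary endpoint, and endpoints are to be compared between randomised groups. This also stands, but the final plan names no by-arm analysis of that endpoint. The link between the targeted list and Section 21.4.1 is itself an inference.

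**The rates are assumed, and a falsely reassuring significant result is not the usual outcome.** With 20% v 5% of survivors affected and mortality 0.20 v 0.40, any SAE is 36% v 43%, about 13 against 15 patients, p = 0.81. The test would significantly favour ZMapp only about 5% of the time. The likelier failure is a null result that hides offsetting effects.

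**A non-fatal comparison has its own bias.** Early deaths may be toxicity, as section 3.8 of the final plan recognises, so deaths cannot be dropped. Death also competes with non-fatal events: with an identical 20% rate in survivors and mortality 0.20 v 0.40, non-fatal SAEs are 0.80 × 0.20 = 16% on ZMapp and 0.60 × 0.20 = 12% on oSOC. That apparent excess comes from survival alone. This is why the any-SAE test should stay and the new comparison should be added beside it.

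**Conclusion.** The concern holds for the any-SAE comparison in 3.9.2. It is likely to be dominated by mortality: deaths are about 63% to 97% of SAE patients over the scenarios tabulated, and the rule on targeted conditions points towards the upper end. If ZMapp lowers mortality, the test can cancel a several-fold excess of non-fatal SAEs; if mortality is equal, it dilutes the excess and does not reverse it. These sizes rest on assumed non-fatal rates, the planning mortality pairs and 36 per arm.

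Two stronger readings are not supported. The requirement to report deaths as SAEs is ordinary safety reporting and is not the fault; the gap is in the analysis. Nor do the documents show that a lower SAE percentage would be presented as proof of safety.

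**What to change.** Keep the rule that deaths are SAEs, and keep Fisher's test on any SAE. Add to 3.9.2, before unblinding:

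1. A by-arm comparison of patients with at least one non-fatal SAE (Fisher's exact test), with deaths in a separate row. Show it with both all-randomised and 28-day-survivor denominators, and interpret it with death as a competing event.
2. The by-arm cumulative incidence of haemorrhage, multi-organ failure and seizures, taken from the daily forms. This gives the secondary endpoint in protocol 18.2.2 the analysis that the final plan lacks.

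The cost is two tables from data already collected, with no change to conduct. The added comparison is itself affected by differential survival and has modest power at about 36 per arm (0.28 to 0.67 in the 0.20 v 0.40 scenarios above), so a non-significant result should not be read as showing that non-fatal harm is absent.
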